In summary, the results from the Phase 1 portion of the study showed that PET imaging with ¹⁸F-DCFPyL in patients with prostate cancer is feasible and safe at a radiation dose that is within acceptable limits for diagnostic PET radiotracers [56].

In the Phase 2 portion of the Jl418 study, the diagnostic performance of ¹⁸F-DCFPyL Injection PET/CT imaging to detect areas of local, nodal and/or distant prostate cancer spread was assessed in 25 patients with clinically localized intermediate or higher risk prostate cancer (clinical stage 2: T2b or GS 2: 7 or PSA 2: 10 ng/mL) prior to undergoing radical prostatectomy with pelvic lymph node dissection (PLND). Areas of intra- and extraprostatic tumor spread identified with ¹⁸F-DCFPyL Injection were compared with postop histopathology as the truth standard.

All 25 subjects included in the analysis had at least high-risk PCa based on pre-surgery clinical, laboratory assessments and biopsy-based histology. ¹⁸F-DCFPyL PET/CT imaging was done 1-7 days before surgery. The analysis was performed at the subject level as well as at the individual right, left side lymph node packet levels (n = 50). Eighteen (72%) subjects had Gleason score 4 + 5 = 9 or 5 + 4 = 9, and 13 (52%) subjects were pT3a and 7 (28%) were pT3b based on whole gland histopathology, and seven (28%) subjects were found to have harbored one or more PCa- positive lymph nodes. A median of 13 (range 4-45) lymph nodes was removed at the time of surgery. Notably, two subjects had bilateral lymph node involvement, resulting in a total of 9 positive lymph packets for the entire study cohort. Positive lymph nodes were typically small, with a median diameter of 3 mm (range 1-12).

Following independent image reads and adjudications, 7 (28%) subjects were confirmed to have 2: 1 site of focal radiotracer within the pelvis consistent with N1 disease. This resulted in a sensitivity and specificity of 71.4% (95% CI 29.0-96.3) and 88.9% (65.3-98.6), respectively, for the presence or absence of metastatic prostate cancer. Similar results were found in the packet-level analysis with a sensitivity of 66.7% (29.9-92.5) and a specificity of 92.7% (80.1-98.5), in good agreement with published ⁶⁸Ga PSMA imaging data [50]. Additionally, the readers determined that 3 (12%) subjects had PET/CT findings consistent with Mla disease (none had Mlb or Mlc). All 3 of these patients had a detectable PSA level within 6 months of surgery.

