- 3. Bone lesions will be considered positive if the uptake is focal and greater than normal marrow uptake.
- 4. Prostate bed and prostate lesions will be considered positive if uptake is focal and greater than background activity of the prostate.

Follow-up imaging:

A chart review will be performed at 3, 6, 9 and 12 months with a plan to communicate with the referring oncologist team regarding the plan for follow-up imaging with a CT, MRI and/or bone scan. If a follow-up imaging is not obtained by 12 months, then imaging will be requested. Interpretation of follow-up imaging will be performed by local read. The follow-up conventional imaging should be the same modality/modalities as the initial staging work-up to allow for reproducible and accurate comparisons.

PET positive findings will be validated as true or false positive as outlined in more detail below. False negative ¹⁸F-DCFPyL PET findings cannot be determined as this would require biopsies of all PET negative lesions that are present on conventional imaging.

¹⁸F-DCFPyL PET validation will be based on follow-up imaging:

- 1. Lymph nodes will be assessed by change in size. PET positive lymph nodes will be considered:
 - a. True positive:
 - If on follow-up imaging within 3-12 months, lymph nodes seen on CT or MRI scan decrease by more than 30% (for patients undergoing systemic treatment of focal therapy at this site) or increase by more than 20% in short axis diameter (with a minimum of 3 mm in change in size).
 - If patients with solitary lymph node regions show a decrease of PSA by greater than 50% after targeted treatment (i.e. external beam radiation) and the lymph nodes do not change in size (less than 30% decrease or less than 20% increase in short axis diameter).

b. False positive:

• If on follow-up imaging within 3-12 months, sites of initial ¹⁸F-DCFPyL PET positive lymph node lesions seen on CT or MRI scan decrease by more than 30% without systemic therapy or focal therapy at this site.

- If PET positive lymph node lesions do not meet the criteria for above false positive or true positive findings.
- 2. Visceral lesions (non-lymph node soft tissue or organ) will be assessed by change in size. PET positive visceral lesions will be considered:
 - a. True positive:
 - If on follow-up imaging within 3-12 months, visceral lesions seen on CT or MRI scan decrease by 30% (for patients undergoing systemic treatment of focal therapy at this site) or increase by 20% in largest diameter.

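### The two lymph-node true-positive rules in section 3.5.1 do not meet, because one carries a 3 mm minimum and the other uses percentages only; nodes in between become false positives.

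*Combined protocol and SAP*

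**What the plan says.** The primary endpoint, per-patient PPV, takes its true and false positives from section 3.5.1. For PET-positive lymph nodes followed by imaging, that section gives two true-positive rules and two false-positive rules.

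- **Size rule (true positive).** On CT or MRI at 3 to 12 months, a node qualifies by shrinking more than 30% in a treated patient. The growth arm is an "increase by more than 20% in short axis diameter (with a minimum of 3 mm in change in size").
- **PSA rule (true positive).** Entry needs a solitary node region, targeted treatment and a PSA fall above 50%. The size condition is that "the lymph nodes do not change in size (less than 30% decrease or less than 20% increase in short axis diameter"). There is no millimetre term.
- **Untreated shrinkage (false positive).** Nodes that "decrease by more than 30% without systemic therapy or focal therapy at this site".
- **Residual rule (false positive).** "If PET positive lymph node lesions do not meet the criteria for above false positive or true positive findings".

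Section 3.10.1 ranks histopathology first, then imaging, then PSA, and assigns validation to unblinded local investigators. The visceral and prostate-bed rules in 3.5.1 use similar percentages but have no 3 mm minimum.

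**The concern.** The PSA rule appears to serve nodes whose size has not changed enough to decide the matter. For that it must begin where the size rule stops. It does not, because the size rule asks for a percentage and an absolute change while the PSA rule asks only whether the percentage is small. A node can therefore change too much for the PSA rule and too little for the size rule, and the residual rule then labels it a false positive.

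If the 3 mm minimum covers decreases, the classification is not monotone in response: a node that shrinks moderately after treatment is scored worse than one that does not shrink at all. The nodes involved are true disease on the protocol's own PSA evidence, so PPV is pushed downward, and a larger sample does not remove the error. The text also leaves open whether the minimum covers both directions, and unblinded readers would have to settle that case by case.

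**Working it through.** **The plan's own precision figure.** Section 3.10.2 expects 300 × 0.85 = 255 positive patients and tabulates exact 95% intervals. Clopper-Pearson intervals for 204, 214, 225, 235, 245 and 255 true positives out of 255 are 74.6–84.7, 78.8–88.2, 83.6–91.9, 88.2–95.1, 92.9–98.1 and 98.6–100%. These round to the plan's table.

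**Where the 3 mm minimum overrides the percentages.** For baseline short axis *b* in mm, 3 mm is 300/*b* percent. It equals 30% at 3/0.30 = 10 mm and 20% at 3/0.20 = 15 mm. If the minimum covers decreases, the shrinkage gap exists for every node under 10 mm and runs from 30% up to 300/*b* percent:

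| Baseline (mm) | Gap in shrinkage |
|---|---|
| 9 | above 30% and below 33% |
| 8 | above 30% and below 37.5% |
| 7 | above 30% and below 43% |
| 6 | above 30% and below 50% |
| 5 | above 30% and below 60% |
| 4 | above 30% and below 75% |

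A 3 mm node would have to vanish to qualify by shrinking, and a smaller one could never qualify that way. On the growth side, the gap covers nodes under 15 mm that grow more than 20% but less than 3 mm.

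**Applying the rules literally.** Conditions: solitary node region, targeted treatment, PSA fall above 50%, no decisive histology.

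| Baseline → follow-up (mm) | Change | Minimum covers both directions | Minimum covers growth only |
|---|---|---|---|
| 6 → 6 | 0% | TP (PSA) | TP (PSA) |
| 6 → 5 | −17%, 1 mm | TP (PSA) | TP (PSA) |
| 6 → 4 | −33%, 2 mm | FP (residual) | TP (size) |
| 6 → 3 | −50%, 3 mm | TP (size) | TP (size) |
| 8 → 10 | +25%, 2 mm | FP (residual) | FP (residual) |
| 8 → 11 | +37.5%, 3 mm | TP (size) | TP (size) |
| 10 → 7 | −30%, 3 mm | FP (residual) | FP (residual) |

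The last row shows the boundary case: the size rule needs more than 30% and the PSA rule needs less than 30%, so exactly 30% meets neither. The same holds for exactly 20% growth.

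**Cost per patient.** If a patient's result rests on the affected node, moving that patient from true to false positive costs 1/255 = 0.39 points. Starting from 225/255 = 88.2% (83.6–91.9), the illustrations below are not estimates, since the documents give no count:

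- 1 patient: 224/255 = 87.8% (83.2–91.6)
- 5 patients: 220/255 = 86.3% (81.4–90.2)
- 20 patients: 205/255 = 80.4% (75.0–85.1)

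A shift equal to the planned half-width at 88%, about 4 points, would take roughly 4/0.39 ≈ 10 patients.

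**The case against.** The strongest reply is that the 3 mm parenthesis directly follows the growth arm, while the decrease arm has its own parenthesis about treatment. If the minimum qualifies growth only, 6 → 4 mm under treatment is a true positive and the shrinkage gap does not exist. This stands as a possible reading. Against it, the parenthesis speaks neutrally of change in size, and the section uses that term for both directions. What survives on the growth-only reading is weaker: a node that grew while PSA fell is discordant evidence, so the complaint that response is penalised does not apply there.

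A reader might infer that any small node that stays the same size is a true positive. The documents do not support that. With more than one node region, without targeted treatment or without the PSA fall, the unchanged node is also a false positive under the residual rule, and the contrast disappears. Histology, where decisive, overrides both rules.

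A reader might also infer a bias of several PPV points from the Johns Hopkins pre-surgical series (section 1.6.1.1): "Positive lymph nodes were typically small, with a median diameter of 3 mm (range 1-12"). That series is not this population. It counts all histology-positive nodes, including some PET missed (packet-level sensitivity 66.7%). The size rule applies only to nodes seen on CT or MRI, and section 1.2 says these methods rely on lesions larger than 1 cm, where there is no shrinkage gap. How many PET-positive nodes in this trial will measure under 10 mm on CT or MRI, and meet all the other conditions, is not given.

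Finally, section 3.10 sets no success threshold for PPV, so the consequence is a biased estimate and not a wrong pass or fail.

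**Conclusion.** The defect is real and lies in the definition of the primary endpoint. The size and PSA rules for nodes are not complements, and the residual rule turns the space between them into false positives. A gap exists on either reading of the 3 mm minimum. The shrinkage gap, where a responding node is scored worse than an unchanged one and PPV is biased downward, requires that the minimum covers decreases. It also requires a solitary node region, targeted treatment, a PSA fall above 50% and no decisive histology. On the growth-only reading, what remains is the small-growth gap and the exact 30% and 20% boundaries.

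The size of the effect on PPV cannot be derived from the documents. The firm figure is 0.39 points per affected patient at 255 positives, assuming that the patient's classification rests on that node.

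**What to change.** In the PSA rule for lymph nodes, replace the percentage description of an unchanged node with: *the node does not meet the size-change criterion in the bullet above, including its 3 mm minimum*. Keep the solitary-region, targeted-treatment and PSA conditions. For nodes meeting those conditions, the two rules then leave no gap on either reading, and the exact 30% and 20% cases are covered. Nodes in patients with more than one region remain outside the PSA rule, as now.

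Separately, state before any lesion is adjudicated whether the 3 mm minimum covers growth only or both directions. It should not be extended to decreases by default. A systemically treated node going from 6 to 4 mm (−33%) is a true positive if the minimum covers growth only. It would become a false positive if the minimum covered both directions, with no PSA route because no targeted treatment was given.

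The cost is one sentence plus one clarification, with no new data or procedures. The downside is that some nodes with small absolute but large percentage growth would be confirmed by PSA: 4 → 6.9 mm is +73% but only 2.9 mm, and would count as not meeting the size criterion.

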Efficacy	PET imaging evaluated qualitatively and semi-quantitatively.
Safety	Patient safety will be evaluated based on incidence and nature of adverse events (AEs) and severe AEs (SAEs) or findings on physical examination.

Name of Sponsor	[name]
Investigational Product	¹⁸ F-DCFPyL
STATISTICAL M	IETHODS AND ANALYSIS
Efficacy	PPV will be estimated by the number of true positives (TP) divided by number of patients who are tested positive (i.e., TP + FP) based on the PET imaging, with the corresponding exact 95% confidence intervals (Cis) being reported. The determination of TP and positive testing is detailed in Section 3.5.1. All patients will be followed up for histopathologic analysis, conventional imaging (CT, MRI and/or bone scan) and/or serum PSA after focal salvage therapy acquired during clinical routine. Combination of (in descending priority) histopathologic analysis, imaging, and PSA follow-up after local/focal therapy will be taken as composite reference standard. Validation will be performed by the unblinded local investigators after reviewing images and reports, following prespecified criteria of the study protocol. In patients with follow-up, positive ¹⁸ F-DCFPyL PET findings will be validated as true or false-positive results. Region negative on ¹⁸ F-DCFPyL PET, but with subsequently confirmed prostate cancer by histopathologic analysis, will be considered false-negative results. True negative will not be defined.
Safety	The safety and tolerability of ¹⁸ F-DCFPyL Injection will be assessed using the incidence, nature, and severity of adverse events up to 1 day following infusion. The maximum grade for each type of toxicity will be recorded for each patient, and frequency tables will be reviewed to determine toxicity patterns.

TABLE OF CONTENTS

				F	Page
SYNC	PSIS				4
ABBR	REVIAT	IONS A	ND DEI	FINITIONS	12
1.	BACK	GROUI	ND AND	ORATIONALE	13
	1.1	INTRO	DUCTION	ON	13
	1.1			eveloping Prostate Cancer Imaging Agents	
	1.3			A for Prostate Cancer Detection	
	1.4			cription of Investigational Product	
	1.5			clinical Studies	
		1.5.1		ry of Pharmacology Studies	
		1.5.2		ry of Pharmacokinetics Studies	
		1.5.3	Determi	nation of Radiation Dose Estimates in Humans	23
		1.5.4	Toxicolo	ogy	
			1.5.4.1	5	
	1.6	Results		cal Studies	
		1.6.1	Previou	s Human Experience	25
			1.6.1.1		
				molecular Weight PSMA based PET Radiotracer, in Patients	
				with Prostate Cancer	25
			1.6.1.2	Study J1545: Pilot Study of ¹⁸ F-DCFPyL PET/CT in the	

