2.2 SECONDARY OBJECTIVE

To determine the PPV of ¹⁸F-DCFPyL PET on a per-region basis, specifically focusing on the prostate or prostate bed, pelvis, extra pelvis, and bones.

2.2.1 Secondary Endpoint

Positive predictive value (PPV) of ¹⁸F-DCFPyL PET on a per-region basis as detailed in Section 3.5.1.

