3.5 ASSESSMENT OF INTERVENTION

3.5.1 Imaging Protocol and Follow up

Patients will be intravenously injected with:::; 333 MBq (:::; 9 mCi) of radiotracer approximately 60 minutes prior to image acquisition and will be imaged using the GE Discovery PET-CT scanner at UPMC Hillman Cancer Center, UPMC Magee-Women's Hospital, or UPMC Shadyside Hospital. The scanner will be operated in three-dimensional (3D) emission mode on CT attenuation correction as the case may be and images will be reconstructed with manufacturer-supplied ordered subset expectation maximization iterative methods without point-spread function. The field of view for ¹⁸F-DCFPyL PET scans will be vertex to mid-thigh.

The PET images will be evaluated qualitatively by UPMC Hillman Cancer Center (HCC) nuclear medicine physicians. PET scans will be randomly assigned between five PET readers. Interpreters will have at least more than 5 years of PET interpretation and will interpret images. Double reading will be performed for all the PET scans. The readers will be provided with the recent PSA levels and the type of primary therapy (prostatectomy vs radiation therapy) but will be blinded to all other information. The report will indicate the localization of detected lesions either in the prostate bed, locoregional lymph nodes, distant lymph nodes, bones, and/or visceral organs. A scan will be deemed 'positive' if at least one lesion suggestive of disease recurrence is noted. Prostate lesions and lymph nodes will be considered positive if the uptake in those lesions exceeds blood pool activity. Bone lesions will be recorded as positive if the activity is higher than normal bone marrow uptake.

The UPMC HCC nuclear medicine physicians have extensive experience in interpreting FDG-PET/CT scans including those performed with a variety of agents currently used in the research setting. Scans will be interpreted using HE AW 3.2 Volume Viewer software package.

Visual interpretation:

1. Lymph nodes will be deemed positive if the PET scan uptake is focal and greater than blood pool (adjacent or mediastinal blood pool). Pelvic lymph nodes will be subclassified

- according to their localization as follows: R/L obturator, R/L external iliac, R/L internal iliac and other (total of 7 subgroups).
- 2. Visceral lesions will be considered positive if the uptake is focal and greater than physiologic background activity of the involvement organ or the anatomic location.

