 - If patients with solitary visceral metastasis show a decrease of PSA by greater than 50% after targeted treatment (i.e. external beam radiation) and lesions do not change in size (less than 30% decrease or 20% increase in largest diameter).

b. False positive:

- If on follow-up imaging within 3-12 months, sites of initial PET positive lesions seen on CT or MRI scan decrease by more than 30% without systemic therapy or focal therapy at this site.
- If ¹⁸F-DCFPyL PET positive lesions do not meet the criteria for above false positive or true positive findings.
- 3. ¹⁸F-DCFPyL PET positive bone lesions will be considered:
 - a. True positive:
 - If there was a corresponding positive sclerotic lesion on the CT portion of the ¹⁸F-DCFPyL PET in the same location as the focal uptake.
 - If there is focal uptake seen on the baseline bone scan performed within one month of ¹⁸F-DCFPyL PET.
 - If there is a lesion noted on the initial MRI imaging scan performed within one month of ¹⁸F-DCFPyL PET.
 - If within 12 months follow-up CT scan demonstrates development of sclerosis.
 - If within 12 months follow-up MRI scan demonstrates a new bone lesion.
 - If within 12 months follow-up bone scan demonstrates new focal uptake.

b. False positive:

- If ¹⁸F-DCFPyL PET positive bone lesions do not meet the criteria for true positive findings.
- 4. ¹⁸F-DCFPyL PET positive prostate bed and prostate lesions will be considered:
 - a. True positive:
 - If on follow-up imaging within 12 months, lesions seen on CT or MRI scan decrease by 30% (for patients undergoing systemic treatment of focal therapy at this site) or increase by 20% in largest diameter.

• If patients with prostate bed lesions show a decrease of PSA by greater than 50% after targeted treatment (i.e. external beam radiation) and lesions do not change in size (less than 30% decrease or 20% increase in largest diameter).

b. False positive:

- If on follow-up imaging within 3-12 months, sites of initial ¹⁸F-DCFPyL PET positive lesions seen on CT or **MRI** scan decrease by more than 30% without systemic therapy or focal therapy at this site.
- If ¹⁸F-DCFPyL PET positive lesions do not meet the criteria for above false positive or true positive findings.

Histopathology/Biopsy:

- 1. Localization of lesions for histopathology/biopsy will be classified according to the regions in table (Definition of regions) below.

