Table: Definition of regions

Region	Description
1	Prostate bed
2	Pelvis outside of prostate bed (including LNs)
3	Extra-pelvic soft tissue lesions, LNs, visceral metastases
4	Osseous metastases

3.5.2 Screening Assessments

Patients determined to meet the eligibility criteria to participate in the study will undergo Screening assessments as per the Study Schedule of Activities in Appendix A. The following screening procedures will be performed:

- Informed Consent will be obtained prior to any study-related procedures
- Eligibility assessment per the inclusion and exclusion criteria and diagnosis confirmation
- Subject demographics
- Prostate cancer history
- Vital Signs

- Physical examination, including height, weight, body mass index (BMI) and ECOG performance status assessment
- List of concomitant medications (hormonal agents only)
- Lab assessments

3.5.3 **Procedure for Registration of Subjects**

Patients must not start study activities prior to registration. Subjects can be enrolled after eligibility criteria are met. Registration will require the following information:

- Date of consent
- Participant's name
- Date of birth
- Primary study physician
- Confirmation of eligibility

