3.10.3 Analysis of Primary and Secondary Endpoints

PPV will be estimated by the number of true positives (TP) divided by number of patients who are tested positive (i.e., TP + FP) based on the PET imaging, with the corresponding exact 95% confidence intervals (Cis) being reported. The determination of TP and positive testing is detailed in Section 3.5.1. Secondary endpoints are the PPV of ¹⁸F-DCFPyL PET (per-region). These will also be estimated as the corresponding percentage and its exact 95% Cis.

The safety profile observed to date suggests that the toxicity of the proposed study product is unlikely to be clinically significant. However, we will monitor toxicity closely. Any patient who has started the studied treatment will be evaluable for safety. The NCI CTCAE version 5.0 defines the term toxicity as adverse events that are classified as either possibly, probably, or definitely related to study treatment. The maximum grade for each type of toxicity will be recorded for each patient, and frequency tables will be reviewed to determine toxicity patterns.

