3.10.4 Missing Data

Missing data will not be imputed except for AE and CONMED missing dates.

3.10.5 Interim Analyses

There is no Data Safety Monitoring Committee or Interim Analysis planned for this study.

4. ETHICS

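### The primary per-patient PPV has conflicting denominators, and no rule turns lesion results into a patient or region result

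*Combined protocol and SAP*

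**What the plan says.** The primary endpoint (2.1.1) is TP/(TP + FP) per patient, and the secondary endpoint (2.2.1) is PPV "on a per-region basis as detailed in Section 3.5.1". Both therefore rest on section 3.5.1.

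**Text that puts unverified positives in the denominator**
- The residual FP bullets in 3.5.1. For nodes: "If PET positive lymph node lesions do not meet the criteria for above false positive or true positive findings". For bone, a finding is FP if "PET positive bone lesions do not meet the criteria for true positive findings". Visceral and prostate lesions have similar bullets.
- The denominator in 3.10.3, repeated in the synopsis and 3.10.1: "number of patients who are tested positive (i.e., TP + FP) based on the PET imaging".
- Section 3.10.1 makes every scanned patient with rising PSA evaluable, and 3.10.2 bases precision on all 255 expected positives.

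**Text that leaves them out**
- The synopsis and 3.10.1 limit validation with the opening "In patients with follow-up, positive".
- The block in 3.5.1 that holds the residual bullets is introduced as validation by follow-up imaging.
- Section 3.10.4: "Missing data will not be imputed except for AE and CONMED missing dates".

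**Aggregation.** Section 3.5.1 calls a scan positive "if at least one lesion suggestive of disease recurrence is noted". That defines the test result, not a TP patient. The region table lists four regions without a rule, and region 3 pools "Extra-pelvic soft tissue lesions, LNs, visceral metastases".

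**The concern.** The study has one primary number. Two analysts who follow different sentences of the plan can compute different values of it from the same data. Missing verification is foreseeable: 3.5.1 makes biopsy depend on clinical feasibility, leaves procedures and imaging to standard of care, and only requests imaging if none was obtained by 12 months.

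The aggregation gap is separate. A patient with one confirmed and one refuted lesion, or one confirmed and one never followed, has no stated patient result, and the same holds within a region. Validation is done by unblinded local investigators (3.10.1), so a rule chosen after lesion results are known would be hard to defend.

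**Working it through.** **Inputs.** 300 evaluable patients, 85% positive, so 0.85 × 300 = 255 (3.10.2). Exact 95% CI with a stated width under 12 points (3.10.2). Verified PPV of 84%, a row of the 3.10.2 table, with 80% and 88% as the range. The unverified share is not in the documents; 5, 10 and 20% are assumptions.

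**1. The plan's own figures.** Clopper-Pearson limits for x of n are the 0.025 quantile of Beta(x, n−x+1) and the 0.975 quantile of Beta(x+1, n−x). At n = 255:
- 204/255 gives 74.6 to 84.7% (width 10.2).
- 214/255 gives 78.8 to 88.2% (width 9.4).
- All six rows reproduce to the whole percent; the 88% row needs 225/255 rather than 224/255.

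The table is correct and the half-width is about 5 points. It supposes that all 255 positives carry a TP or FP label.

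**2. Denominator.** With u unverified, n = 255 − u and TP ≈ 0.84n. Verified-only is TP/n, counted as FP is TP/255, and counted as TP is (TP + u)/255.

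| u (share) | Verified-only | Counted as FP | Gap (points) | Counted as TP |
|---|---|---|---|---|
| 13 (5%) | 203/242 = 83.9% | 203/255 = 79.6% | 4.3 | 216/255 = 84.7% |
| 25 (10%) | 193/230 = 83.9% | 193/255 = 75.7% | 8.2 | 218/255 = 85.5% |
| 51 (20%) | 171/204 = 83.8% | 171/255 = 67.1% | 16.8 | 222/255 = 87.1% |

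Verified-only against counted as FP, for the same three shares:
- Verified PPV of 80%: 80.2/76.1, 80.0/72.2 and 79.9/63.9%.
- Verified PPV of 88%: 88.0/83.5, 87.8/79.2 and 88.2/70.6%.

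**3. Aggregation.** The documents give neither lesions per patient nor lesion-level PPV, so this is only an illustration. Assume lesion PPV q = 0.85 and two lesions in a patient.
- Independent lesions: at least one TP = 1 − 0.15² = 97.8%; both TP = 0.85² = 72.3%.
- Within-patient correlation 0.5: both TP = 0.7225 + 0.5 × 0.85 × 0.15 = 78.6%; at least one TP = 1 − (0.0225 + 0.06375) = 91.4%.

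The choice of rule matters for patients with several lesions. How far it moves the overall PPV depends on how many such patients there are.

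**4. Baseline bone criteria.** A bone lesion is TP if it has a sclerotic correlate on the PET's own CT, or uptake or a lesion on a bone scan or MRI within one month. Without follow-up, these criteria can confirm but cannot refute. If 10 of the 25 unverified patients above entered through them alone (an assumption), 193/230 = 83.9% becomes 203/240 = 84.6%.

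**5. Window (a note).** The imaging criteria work within 3-12 or 12 months. A scan requested because none was obtained by 12 months would normally fall outside. The residual bullet, read literally, then makes the lesion FP unless histopathology, the PSA criterion or a baseline bone criterion applies. The documents do not say how many patients would depend on that scan.

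**The case against.** The best defence is that the plan, read as a whole, already means verified-only. The residual bullets sit in a block about follow-up imaging, labels are assigned to patients with follow-up, and nothing is imputed, so an unfollowed patient has no label. Nor can the bullets be applied literally throughout. No TP list in 3.5.1 includes a positive biopsy, so a biopsy-proven node without qualifying imaging or PSA would be FP, although histopathology ranks first in the composite standard. This stands: verified-only is the more natural reading. It does not settle the matter, because the stated denominator, the evaluability sentence and the sizing on 255 all point the other way.

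It is also fair that the size rests on assumed shares. A reader might take the cited phase 3 trial's unevaluable positives (section 1.1: 33/137 = 24.1%, 24/124 = 19.4%, 24/123 = 19.5%) as the expected share. They are only a loose proxy. That count includes lesion-level false negatives, and those patients had negative or equivocal standard imaging (section 1.4), which this trial does not require.

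Two further inferences are not supported:
- A reader might infer that the PSA criteria, like the baseline bone criteria, can only confirm. Each also requires that the lesion did not change in size, so follow-up imaging is needed. A size-stable lesion without the PSA fall becomes FP through the residual bullet.
- A reader might fill the aggregation gap with the rule of at least one confirmed lesion in sections 1.1 and 1.2. That rule defines the cited trial's endpoint. Section 1.2 presents this study's PPV as a different perspective and does not adopt it.

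**Conclusion.** The point holds and should be fixed before analysis. The plan contains two denominators for its only primary endpoint, and it has no rule from lesion to region or patient. The literal reading lowers the primary PPV by 4.3 to 16.8 points relative to verified-only at 5 to 20% unverified and a verified PPV of about 84%. From 10% unverified the gap exceeds the planned half-width. Those shares are assumptions, and the aggregation effect cannot be sized from the documents.

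A reader might infer that the trial's conclusion could reverse. It could not, because the study is estimation-only with no success threshold. What changes is the reported estimate. The catch-all for lesions that were followed is clearly stated and is not in dispute.

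**What to change.** 1. Define the primary PPV as TP/(TP + FP) among PET-positive patients with a reference standard: histopathology, follow-up imaging that can be judged under 3.5.1 (with PSA where 3.5.1 uses it), or a baseline bone criterion. Report how many positives have none, with bounds that count all of them as FP and all as TP.
2. Keep the residual FP rule for followed lesions, and state that it does not apply to lesions with no follow-up.
3. State one lesion-to-region and one region-to-patient rule. For example, at each level: TP if at least one is TP, FP if none is TP and all are determinate, otherwise indeterminate. Also report the analysis that counts FP-plus-indeterminate patients as FP, because this rule shifts the estimate too. If 13 of 255 were such patients (an assumption), 214/242 = 88.4% compares with 214/255 = 83.9%.
4. Report a sensitivity analysis without patients verified only by the baseline bone criteria.
5. Reconcile the 12-month imaging request with the validation windows in 3.5.1 and the one-year follow-up column in Appendix A. State whether a scan outside the window is classified or treated as no follow-up, so that it does not become FP by default.

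**Cost.** Protocol and SAP wording, plus a few added analyses. The denominator shrinks: at 20% unverified, 171/204 has exact limits of 78.0 to 88.6%, a width of 10.6 points, still under the stated 12. Verified patients are a selected group, and the bounds in item 1 show how much that could matter.
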